### 2.1. Multiplicity Adjustment

Given the small sample size and open-label nature of the study, no multiplicity adjustments will be made to control for family-wise type 1 error.

### 3. Analysis Sets

Participant Analysis Set	Description
Full	

• All participants enrolled and with at least one administration of IP, will be included in this analysis set. The Full Analysis set will be used to analyze the efficacy and safety endpoints.

This document, including any source code, is the property of [Clinvest Research LLC](#), and may contain proprietary, confidential, or legally privileged information. No part of this report, or any information contained therein, may be disseminated without the written consent of [Clinvest Research LLC](#).

## 4. Statistical Analyses

### 4.1. General Considerations

- An alpha of .05 will be used for statistical significance for all statistical tests.
- All statistically significant multivariate analyses will be followed by univariate post-hoc tests.
- Univariate post-hoc tests will utilize appropriate multiple comparison adjustments (Bonferroni, Tukey, etc.) as needed.
- If a variable name (e.g., from REDCap Cloud or Fitabase) is directly used in this document, it will appear in this format: **[VARIABLE]**
- 95% Confidence Intervals will be used when necessary.

#### 4.1.1. Missing Data

Missing data for full analysis population participants will be imputed as follows:

- Missing values on questionnaire items will be handled according to the questionnaire's scoring manual. When no guidance is specified in a questionnaire scoring manual, missing items will be left null and the score and/or sub-score will be imputed using a last observation carried forward (LOCF) method. This type of imputation replaces the missing value with the last observation value obtained for the participant.
- Missing DHD entries (Monthly Migraine Days) will be imputed as follows:
  - < 14 DHDs completed: Participant's average MMDs for that study period will be replaced with their last study period's MMD using the LOCF method.
  - $\geq 14$  DHDs completed: Participant's average MMDs for that study period will be imputed based on the data available in that study period and prorated to 28 days.
- Missing Garmin data (Steps and Sleep) will be imputed as follows:
  - < 14 days synced: Participant's average steps and/or sleep for that study period will be replaced with their last study period's steps and/or sleep using the LOCF method.
  - $\geq 14$  days synced: Participant's steps and/or sleep for the missing day will be imputed using the participant's mean steps and/or sleep for the data available in that study period.

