#### **4.3.3. Change in Migraine Interictal Burden Scale (MIBS-4) Scores from Baseline to Each 4-Week Treatment Period**

##### **4.3.3.1. Definition of Endpoint**

The MIBS-4 is a 4-item, self-administered questionnaire which measures interictal migraine-related burden in 4 domains: impairment in work or school, impairment in family and social life, difficulty making plans or commitments, and emotional/affective and cognitive distress. The MIBS-4 total score is derived from the summation of all four questions on each MIBS-4. Answer options for the MIBS-4 are coded as: 0 = *Don't know/NA*, 0 = *Never*, 1 = *Rarely*, 2 = *Some of the time*, 3 = *Much of the time*, 4 = *Most or all of the time*. The range of total MIBS-4 score for each

This document, including any source code, is the property of [Clinvest Research LLC](#), and may contain proprietary, confidential, or legally privileged information. No part of this report, or any information contained therein, may be disseminated without the written consent of [Clinvest Research LLC](#).

time point is 0 to 12 (with higher scores indicating severe interictal burden of migraine on the participant's daily activities).

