#### **4.4.2. Change in Functional Assessment of Migraine Scale (FAMS) Total Scores from Baseline to Each 4-Week Treatment Period**

##### **4.4.2.1. Definition of Endpoint**

Two versions of the Functional Assessment of Migraine Scale (FAMS) were administered to participants, including Research (FAMS-R) and Research Supplement (FAMS-RS). FAMS total score consists of all 27-items from both FAMS-R and FAMS-RS, self-administered in the form of a questionnaire, which evaluates the complete patient with migraine and their response to treatment. The FAMS total score is derived from the summation of all 27 questions. The range of total FAMS score is 27 to 135 (with lower scores indicating greater daily life burdens due to migraine).

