### 6.3.1.2. Missing Data Imputation Guidelines

#### 6.3.1.2.1. Item-Level Missing Data

**For each MFIQ domain, if <50% of the items within a domain are missing, the mean of the item scores that are present for that day is used to impute a score for the missing item(s). If ≥50% of the items that make up a domain are missing, no domain score is calculated; the domain score is considered missing.**

**For the purposes of domain scoring, “does not apply” (DNA response) are not considered missing and will be imputed with the mean of other non-missing items in the domain.**

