**Figure 6. BMWS Questionnaire**

#### 6.3.6.1. Scoring

The BMWS total score is derived from the summation of all eight questions. Answer options for the BMWS are coded as: 0 = *Not true at all*, 1 = *Somewhat true*, 2 = *Moderately true*, 3 = *Definitely true*. The range of total BMWS score is 0 to 24 (with higher scores indicating more worry within the participant).

This document, including any source code, is the property of [Clinvest Research LLC](#), and may contain proprietary, confidential, or legally privileged information. No part of this report, or any information contained therein, may be disseminated without the written consent of [Clinvest Research LLC](#).

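### For FAMS and BMWS (and MIBS-4 if its manual is silent), SAP 4.1.1 sets no minimum-items threshold, so one blank item replaces the current score with the previous visit's

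*SAP*

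**What the plan says.** SAP 4.1.1 first defers to each questionnaire's scoring manual. Where the manual is silent, "missing items will be left null and the score and/or sub-score will be imputed using a last observation carried forward (LOCF) method". The next sentence explains the method: "This type of imputation replaces the missing value with the last observation value obtained for the participant". The section does not say how many items must be blank before this happens.

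Three scales are sums of their items:
- FAMS (SAP 4.4.2.1): "The FAMS total score is derived from the summation of all 27 questions".
- BMWS (SAP 6.3.6.1): "The BMWS total score is derived from the summation of all eight questions".
- MIBS-4 (SAP 4.3.3.1): "The MIBS-4 total score is derived from the summation of all four questions on each MIBS-4".

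Appendix 6.3 sets out the FAMS and BMWS items and scoring in full, and neither deals with a blank. Guidance on blanks appears there only for the MFIQ domains, in 6.3.1.2.1: "if <50% of the items within a domain are missing, the mean of the item scores that are present for that day is used".

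In the Schedule of Activities, FAMS, BMWS and MIBS-4 are first given at Visit 2. Only the MFIQ is also given at Visit 1. Protocol 8.1 has the questionnaires completed electronically in the clinic and does not say whether every item must be answered.

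**The concern.** Read as written, a participant who answers 26 of 27 FAMS items at Visit 3 is analysed with the Visit 2 total. The post-treatment answers are set aside and the change is exactly zero. At later visits the copied value is usually post-treatment, but it still belongs to another month and is then analysed as if observed at this one.

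The rule is also out of step with the rest of the SAP. MFIQ domains are scored from that day's answers when fewer than half are missing. Section 4.1.1 itself uses same-period data for diaries and for the activity tracker once 14 days are available. (Section 4.3.4.2 sets a different diary threshold, which is a separate matter.) Only questionnaires without manual guidance lose a nearly complete current record.

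Blanks are plausible. FAMS-R item 6 asks about missing work and offers no option for someone without a job. Employment is not an entry criterion, and WPAI-M question 1 asks about it. Such a participant could leave item 6 blank at every visit and never have a FAMS total.

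**Working it through.** **Plan's own figure.** The SAP gives no number on this point. Its one computed design figure, 54 participants, reproduces: a two-sided paired t-test with d = 0.50 and alpha 0.05 has power 0.9502 at n = 54 (noncentral t). Nothing below depends on it.

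**Inputs.** Items per score: FAMS total 27, BMWS 8, MIBS-4 4 (SAP 4.4.2.1, 6.3.6.1, 4.3.3.1). FAMS subscales: Functioning 16, Medicine 2, and three of 3 items each (SAP 4.4.3.1). The blank rate per item, p, is not in the documents. I assume 0.5, 1 and 2%, independent across items.

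**Step 1: forms with at least one blank.** q = 1 − (1 − p)^k.

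| Score | k | p = 0.5% | p = 1% | p = 2% |
|---|---|---|---|---|
| FAMS total | 27 | 12.7% | 23.8% | 42.0% |
| BMWS | 8 | 3.9% | 7.7% | 14.9% |
| MIBS-4 | 4 | 2.0% | 3.9% | 7.8% |

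A form with exactly one blank loses 26 of 27 answers (96%) for the FAMS total, 7 of 8 for BMWS and 3 of 4 for MIBS-4.

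**Step 2: effect on mean change.** Let c3, c4 and c5 be the true mean changes at Visits 3 to 5, with baseline observed and blanks unrelated to outcome. The expected analysed changes are:
- V3 = (1 − q)·c3
- V4 = (1 − q)·c4 + q·V3
- V5 = (1 − q)·c5 + q·V4

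For the FAMS total at p = 1% (q = 0.238), Visit 3 gives V3/c3 = 0.762 whatever the trajectory, so a true mean gain of 10 points is analysed as about 7.6. Visit 5 depends on an assumed trajectory:

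| Assumed c3, c4, c5 | V5/c5, FAMS | V5/c5, BMWS |
|---|---|---|
| Gradual: 0.60, 0.85, 1.00 | 0.94 | 0.99 |
| Plateau: 1.00, 1.00, 1.00 | 0.99 | 1.00 |
| Waning: 1.00, 0.90, 0.70 | 1.06 | 1.02 |

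Gradual case for FAMS: V3 = 0.762 × 0.60 = 0.457; V4 = 0.762 × 0.85 + 0.238 × 0.457 = 0.757; V5 = 0.762 × 1.00 + 0.238 × 0.757 = 0.942.

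**Step 3: missing baseline.** At p = 1%, 54 × 0.238 ≈ 13 participants would have an incomplete FAMS at Visit 2, with no earlier score to carry.

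**Step 4: after the fix, p = 1%.** Scores still missing are those with 50% or more of items blank.
- BMWS, 4 or more of 8: less than 0.001%.
- MIBS-4, 2 or more of 4: 0.06%.
- FAMS subscales: Medicine, 1 or more of 2, is 1 − 0.99² = 1.99%. Each 3-item subscale, 2 or more of 3, is 3 × 0.01² × 0.99 + 0.01³ = 0.03%. Functioning, 8 or more of 16, is negligible.
- FAMS total: 1 − 0.9801 × (1 − 0.000298)³ = 2.1%, against 23.8% now. Almost all of it comes from the two-item Medicine subscale, where one blank is already 50%.

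**The case against.** The size may be nil. The forms are electronic and completed in the clinic, and if they force an answer the rule never operates. That SAP 4.1.1 plans for missing items says nothing about how often they occur. Independence is also assumed: at the same per-item rate, blanks clustered in the same forms would give smaller shares than those in Step 1. All of this stands, and the percentages are illustrations.

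The trigger is not equally firm for the three scales. For MIBS-4, the scoring key in Appendix 6.3.2 is a figure not shown in the text reviewed, so its silence on blanks is unconfirmed. Its Don't know/NA option, scored 0, also gives an unsure respondent something to tick. This stands, and MIBS-4 is included only conditionally.

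A reader might infer that the rule pulls change toward zero throughout. The documents support that only at Visit 3, where baseline is carried; Step 2 shows the Visit 5 effect going either way. A reader might also infer that one blank voids the whole questionnaire. SAP 4.1.1 speaks of the score and/or sub-score, so FAMS subscales without the blank item keep their current values.

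Proration is also a larger assumption here than for the MFIQ, whose domains are reported to be unidimensional. The FAMS total mixes functioning, medicine, finance, provider and education items, and the MIBS-4 items cover four different areas. This is why the FAMS remedy should work within subscales.

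**Conclusion.** The concern holds, with limits. For FAMS and BMWS, and for MIBS-4 if its manual is silent, the rule as written lets one blank replace the affected current score with an older one. That sets the change to zero at Visit 3, has an effect of unknown direction at Visits 4 and 5, and is undefined at Visit 2.

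The FAMS total is most exposed because it has the most items, but it is exploratory. BMWS and MIBS-4 are the secondary endpoints concerned, and their exposure is smaller. Every percentage rests on an assumed, independent blank rate.

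The point does not reach the primary endpoint, which is a single MFIQ item with no other answers to lose, or the MFIQ domains, which have their own rule. SDSF and GSE-SF go through an external scoring service whose handling of blanks the documents do not give, so nothing can be concluded about them. The correction should be made, but it does not threaten the trial's main result.

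**What to change.** Add to SAP 4.1.1, for FAMS, BMWS and MIBS-4 where the manual is silent:

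- When fewer than 50% of the items are missing, score the scale from the items answered at that visit (person-mean proration). For FAMS, apply this within each subscale and take the total as the sum of the prorated subscales.
- Only when 50% or more are missing, treat the score as missing and handle it by the SAP's missing-score rule.
- State how a Visit 2 score that is still missing is handled, since nothing precedes it.
- Do not apply proration to the WPAI-M, whose outcomes are ratios rather than sums.

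The sponsor should also record whether the electronic forms force every answer. If they do, the rule is seldom needed.

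The cost is a few lines of SAP text and minor code; the sample size is unchanged. The downside is that proration assumes the answered items represent the blank ones. One blank in the two-item FAMS Medicine subscale would still make that score, and so the FAMS total, missing.

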### 4.2. Primary Endpoint Analysis

Data for the primary endpoint will be statistically analyzed via a within groups, repeated measures *t*-test, comparing change in participant's MFIQ Global Item Overall Impact on Usual Activities (item # 16) scores from baseline (Visit 2) to the final 4-week treatment period (Visit 5).

This document, including any source code, is the property of [Clinvest Research LLC](#), and may contain proprietary, confidential, or legally privileged information. No part of this report, or any information contained therein, may be disseminated without the written consent of [Clinvest Research LLC](#).

#### **4.2.1. Definition of Endpoint**

The MFIQ is a 26-item self-report questionnaire. It is designed to measure the impact of migraine on physical, social, and emotional functioning over 4 domains: Physical Function (PF), Usual Activities (UA), Social Function (SF), and Emotional Function (EF). **A single global item, Overall Impact on Usual Activities, assessing overall difficulty doing everyday activities is scored separately.** Final transformed scores range from 0-100, with higher scores indicating more impact on the participant. For this endpoint we will be measuring changes in participant's response on the single MFIQ Global Item Overall Impact on Usual Activities (item # 16). The item's transformed score can range from 0-100, with higher scores indicating more impact on the participant.

#### **4.2.2. Main Analytical Approach**

The MFIQ Global Item Overall Impact on Usual Activities is defined as item #16 on the MFIQ. Only data from those participants who meet criteria for the Full Analysis set will be analyzed. Missing data will be imputed as outlined in the Migraine Functional Impact Questionnaire User Manual and Scoring Guide Version 1.0 (Appendix 6.3.1). The scores used to measure the primary endpoint will be taken using the participant's self-reported data entered into the MFIQs administered at Visit 2 and Visit 5 (or Early Discontinuation). The null hypothesis of this study is that participants' global MFIQ overall impact on usual activities item score will not be statistically different from baseline (Visit 2) to End of Study (Visit 5 or Early Discontinuation) after 3 months dose of 140 mg erenumab-aoee.

### **4.3. Secondary Endpoint Analysis**

Data for each of the secondary outcome measures will be statistically analyzed for within group changes using repeated measures *t*-tests and/or repeated measures analysis of variance (ANOVA) with follow-up univariate tests as appropriate.

#### **4.3.1. Change in Migraine Functional Impact Questionnaire (MFIQ) Domain Scores from Baseline to the Final 4-Week Treatment Period**

##### **4.3.1.1. Definition of Endpoint**

The MFIQ is a 26-item self-report questionnaire. It is designed to measure the impact of migraine on physical, social, and emotional functioning over 5 domains: Physical Function (PF), Usual Activities (UA), Overall impact on Usual Activities, Social Function (SF), and Emotional Function (EF). Final transformed scores range from 0-100, with higher scores indicating more impact on the participant. The specific domain scores to be analyzed for this endpoint include impact on Physical Functioning (PF), impact on Usual Activities (UA), impact on Emotional Functioning (EF), and impact on Social Functioning (SF).

#### **4.3.1.2. Main Analytical Approach**

MFIQ domain scores will be derived as outlined in the Migraine Functional Impact Questionnaire User Manual and Scoring Guide Version 1.0 (Appendix 6.3.1). Only data from those participants who meet criteria for the Full Analysis set will be analyzed. Missing data will be imputed as outlined in the Migraine Functional Impact Questionnaire User Manual and Scoring Guide Version 1.0 (Appendix 6.3.1). Data will be statistically analyzed via within groups, repeated measures *t*-tests, comparing change in participant's specific MFIQ domain scores from baseline (Visit 2) to End of Study (Visit 5 or Early Discontinuation).

#### **4.3.2. Change in Migraine Functional Impact Questionnaire (MFIQ) Global and Domain Scores from Baseline to Each 4-Week Treatment Period**

##### **4.3.2.1. Definition of Endpoints**

The MFIQ is a 26-item self-report questionnaire. It is designed to measure the impact of migraine on physical, social, and emotional functioning over 5 domains: Physical Function (PF), Usual Activities (UA), Overall impact on Usual Activities, Social Function (SF), and Emotional Function (EF). Final transformed scores range from 0-100, with higher scores indicating more impact on the participant. For this endpoint we will be measuring participant's response on the single MFIQ Global Item Overall Impact on Usual Activities (item # 16), as well as impact on the Physical Functioning (PF), Usual Activities (UA), Emotional Functioning (EF), and Social Functioning (SF) domains.

##### **4.3.2.2. Main Analytical Approach**

Global as well as the specific MFIQ domain scores will be derived as outlined in the Migraine Functional Impact Questionnaire User Manual and Scoring Guide Version 1.0 (Appendix 6.3.1). Only data from those participants who meet criteria for the Full Analysis set will be analyzed. Missing data will be imputed as outlined in the Migraine Functional Impact Questionnaire User Manual and Scoring Guide Version 1.0 (Appendix 6.3.1). Data will be analyzed via a repeated measures ANOVA comparing change in participant's global and specific MFIQ domain scores from baseline (Visit 2) to each of the 4-week treatment periods (Visit 3, 4, and 5). Significant changes will be followed up using within groups, repeated measures *t*-tests as needed.

#### **4.3.3. Change in Migraine Interictal Burden Scale (MIBS-4) Scores from Baseline to Each 4-Week Treatment Period**

##### **4.3.3.1. Definition of Endpoint**

The MIBS-4 is a 4-item, self-administered questionnaire which measures interictal migraine-related burden in 4 domains: impairment in work or school, impairment in family and social life, difficulty making plans or commitments, and emotional/affective and cognitive distress. The MIBS-4 total score is derived from the summation of all four questions on each MIBS-4. Answer options for the MIBS-4 are coded as: 0 = *Don't know/NA*, 0 = *Never*, 1 = *Rarely*, 2 = *Some of the time*, 3 = *Much of the time*, 4 = *Most or all of the time*. The range of total MIBS-4 score for each

This document, including any source code, is the property of [Clinvest Research LLC](#), and may contain proprietary, confidential, or legally privileged information. No part of this report, or any information contained therein, may be disseminated without the written consent of [Clinvest Research LLC](#).

time point is 0 to 12 (with higher scores indicating severe interictal burden of migraine on the participant's daily activities).

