#### 4.3.3.2. Main Analytical Approach

See Appendix 6.3.2 for MIBS-4 scoring information. Only data from those participants who meet criteria for the Full Analysis set will be analyzed. Data for this secondary endpoint will be analyzed via a repeated measures ANOVA comparing changes in participant's Migraine Interictal Burden Scale (MIBS-4) scores from baseline (Visit 2) to each of the 4-week treatment periods (Visit 3, 4, and 5). Significant changes will be followed up using within groups, repeated measures *t*-tests as needed.

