### Example:

### Item 1: Some of the time (x2)

## Item 2: Never (x0)

### Item 3: Much of the time (x3)

#### Item 4: Rarely (x1)

Total MIBS-4 score:  $1 \times 2 + 1 \times 0 + 1 \times 3 + 1 \times 4 = 2 + 0 + 3 + 4 = 9$ . This would be Se burden

REDCap Cloud Variables used for this analysis: **[MIBS-1]**, **[MIBS-2]**, **[MIBS-3]**, **[MIBS-4]**

This document, including any source code, is the property of [Clinvest Research LLC.](#), and may contain proprietary, confidential, or legally privileged information. No part of this report, or any information contained therein, may be disseminated without the written consent of [Clinvest Research LLC.](#)

REDCap Cloud values for each response are recorded as the participants answer, e.g., ‘Rarely’ instead of with the PRO’s assigned value. In the figure above the red box indicates the value for each response. In R the biostatistician will programmatically recode the responses into the following values to match the PRO’s:

- Don’t Know/NA = 0
- Never = 0
- Rarely = 1
- Some of the time = 2
- Much of the time = 3
- Most or all of the time = 3

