**Example:**

Question 1 = Yes (1) No (0)

Question 2 = 5 hours missed due to Migraine

Question 3 = 0 hours missed for other reasons

Question 4 = 35 hours worked

Question 5 = 6

Question 6 = 3

Percent work time missed due to migraine:  $Q2/(Q2+Q4) = 5/(5+35) = 5/40 = 0.125 \times 100 = 12.5\%$

Percent impairment while working due to migraine:  $Q5/10 = 6/10 = 0.6 = 60\%$

Percent overall work impairment due to migraine:  $Q2/(Q2+Q4)+[(1-( Q2/(Q2+Q4)))x(Q5/10)] = 5/(5+35) + [(1-(5/(5+35)))x(6/10)] = 5/40+[(1-(5/(40)))x(0.6)] = 0.125+[(1-0.125)x(0.6)] = 0.125+[(0.875)x(0.6)] = 0.125+0.525 = 0.525 \times 100 = 52.5\%$

This document, including any source code, is the property of [Clinvest Research LLC](#), and may contain proprietary, confidential, or legally privileged information. No part of this report, or any information contained therein, may be disseminated without the written consent of [Clinvest Research LLC](#).

Percent activity impairment due to migraine:  $Q6/10 = 3/10 = .3 = 30\%$

Results from example: This participant missed 12.5% of work due to migraine and while working their impairment was 60%. Their overall work impairment due to migraine was 52.5%. They also experienced 30% migraine impairment for other activities.

REDCap Cloud Variables used for this analysis: **[WPAIM\_1], [WPAIM\_2], [WPAIM\_3], [WPAIM\_4], [WPAIM\_5], [WPAIM\_6]**

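### SAP 4.3.3.1 codes the top MIBS-4 answer 4, against its own 0–12 range and the recode of 3 in Appendix 6.3.2; two worked scoring examples are also wrong (minor)

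*SAP*

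**What the plan says.** **MIBS-4 coding.** SAP 4.3.3.1 defines the total as the sum of four items. It codes the two lowest answers 0, the next three 1, 2 and 3, and the top one "4 = *Most or all of the time". The paragraph ends with the range for each "time point is 0 to 12". Section 4.3.3.2 then directs the programmer elsewhere: "See Appendix 6.3.2 for MIBS-4 scoring information". Appendix 6.3.2 states that "In R the biostatistician will programmatically recode the responses into the following values", and its list ends with "Most or all of the time = 3", the same value it gives to the next-highest answer. The appendix also says "In the figure above the red box indicates the value for each response", but that figure is not visible in the text reviewed. The exploratory FAMS correlations point both ways: 4.4.3.1 cites 4.3.3.1 for MIBS-4, while 4.4.3.2 cites Appendix 6.3 for scoring.

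**MIBS-4 example.** Appendix 6.3.2 lists four responses worth 2, 0, 3 and 1, the last being "Item 4: Rarely (x1"). The sum beneath uses 4 for that item and reports 9.

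**WPAI-M example.** The last step for overall work impairment in Appendix 6.3.3 reads "0.125+0.525 = 0.525". The resulting 52.5% is repeated in the interpretation below it.

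**The concern.** A scoring rule in an endpoint definition should yield one number from one set of answers. Here the definition and the programming instruction disagree on the top category of a secondary endpoint. The definition also contradicts itself, because its codes cannot produce its range. Someone programming from 4.3.3.1, or writing an independent check from it, would obtain different totals from someone using the appendix. They would also obtain different changes from baseline whenever use of the top category shifts between visits. MIBS-4 and WPAI-M scores also enter the exploratory FAMS correlations.

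The worked examples derive no score themselves, but they are what a programmer would naturally test code against. Correct code would fail both. The SAP version history records only a missing-data revision for version 2, so no scoring correction is on record.

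**Working it through.** **1. MIBS-4 range.** Inputs: four items summed; stated range 0–12 (4.3.3.1); top code 4 (4.3.3.1) or 3 (Appendix 6.3.2). Maximum total = number of items × highest code.

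- With the appendix code: 4 × 3 = 12. The stated range reproduces.
- With the 4.3.3.1 code: 4 × 4 = 16. The range would be 0–16, and the stated range does not reproduce.

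**2. Effect on a participant's score.** The codings differ only in the top category, by 4 − 3 = 1 point per item. A total is therefore 0 to 4 points higher under 4.3.3.1. One item moving from the top to the next-highest answer scores 3 − 4 = −1 under 4.3.3.1 and 3 − 3 = 0 under the appendix.

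**3. Effect on mean change.** Let p be the share of item answers in the top category at a visit. Then

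(mean change under 4.3.3.1) − (mean change under 6.3.2) = 4 × (p at the later visit − p at Visit 2).

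The documents give no values for p, so these falls are assumptions:

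- no change: 0
- fall of 5 percentage points: 4 × (−0.05) = −0.2
- fall of 10 percentage points: 4 × (−0.10) = −0.4
- fall of 20 percentage points: 4 × (−0.20) = −0.8

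These differences arise only if 4.3.3.1 is the section programmed.

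**4. MIBS-4 example.** As printed, 2 + 0 + 3 + 4 = 9. From the responses listed, 2 + 0 + 3 + 1 = 6, so the printed total is 9 − 6 = 3 points too high. The fourth response is worth 1 in both sections, so the answer is 6 under either coding. This error is separate from the coding conflict.

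**5. WPAI-M example.** Inputs from Appendix 6.3.3: Q2 = 5, Q4 = 35, Q5 = 6, Q6 = 3.

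- Work time missed: a = 5/(5 + 35) = 0.125, or 12.5% (as printed)
- Impairment while working: b = 6/10 = 0.60, or 60% (as printed)
- Overall work impairment: a + (1 − a)b = 0.125 + 0.875 × 0.6 = 0.125 + 0.525 = 0.65, or 65% (printed 52.5%)
- Activity impairment: 3/10 = 0.30, or 30% (as printed)

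The printed figure is 65 − 52.5 = 12.5 percentage points too low. As a check, [a + (1 − a)b] − b = a(1 − b) = 0.125 × 0.4 = 0.05, which is never negative for valid inputs. The overall score cannot fall below b = 60%, so 52.5% is impossible under the SAP's formula; 60% + 5% = 65%.

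**6. WPAI-M edge cases.** If Q2 = Q4 = 0, the work-time ratio is 0/0 and undefined. If Q2 > 0 and Q4 = 0, the ratio is Q2/Q2 = 1 and overall impairment is 1 + 0 × Q5/10 = 1, a defined score of 100%.

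**The case against.** The best defence is that the operative instruction is already right. Section 4.3.3.2 sends scoring to the appendix, the appendix prints the recode, and the recode agrees with the stated range. Both example errors are plain on their face, and neither example generates data. This largely stands, and it is why the point is minor. It does not remove the defect. The endpoint definition is still wrong as written, 4.4.3.1 refers back to it, and no higher document settles the matter: Protocol 8.1.2 gives no coding, and Protocol 9.4 lets the SAP prevail.

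Some stronger readings are tempting but unsupported:

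- A reader might infer that the MIBS-4 analysis will be mis-scored. The documents do not show that; the stated R recode gives the 0–12 score.
- A reader might take the 4 in the appendix example as support for a top code of 4. In that example the 4 is attached to an answer worth 1, so it says nothing about the top category.
- A reader might conclude that the WPAI-M formula is wrong. It is not; only the final addition is.
- A reader might want participants with no work hours excluded from the work-based scores. The documents do not set such a rule. Read literally, it could drop someone who missed all work because of migraine, whose score is defined as 100%. Nor can one say flatly that a missing WPAI-M score is carried forward. SAP 4.1.1 defers first to the scoring manual and uses LOCF only where the manual is silent; the full manual is not among the documents.

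Two related items are clarifications, not errors of substance. Section 4.3.5.2 analyses a WPAI-M total, whereas 6.3.3 defines four percentages and no total. The word may be template text, since it also appears for SDSF, GSE-SF and BMWS, and 4.3.5.1 speaks of scores in the plural. The SDSF variable list in 6.3.4 names seven variables for an eight-item form, but the 8–40 range and the conversion table already fix eight items.

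**Conclusion.** The point holds as a minor correction. The code of 4 in 4.3.3.1 contradicts its own range and the appendix recode, and those two agree on 3. Totals would be 0 to 4 points too high if 4.3.3.1 were programmed, with a difference in mean change that depends on unknown top-category shares. There is no effect if the recode is followed. The two examples are wrong whichever coding applies: 6 rather than 9, and 65% rather than 52.5%. The primary endpoint (MFIQ item 16) and N = 54 do not depend on any of this. That 3 is the intended code rests on the internal agreement of the SAP; the Figure 2 key could not be seen. The contradiction itself does not depend on that figure.

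**What to change.** Corrections:

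- In 4.3.3.1, code the top answer 3 and confirm it against the Figure 2 key.
- In 6.3.2, correct the example to 1×2 + 1×0 + 1×3 + 1×1 = 6 and recheck the burden label attached to it.
- In 6.3.3, correct the example to 65% in both the calculation and the interpretation.

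Clarifications while the document is open:

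- In 4.3.5.2, replace the reference to a WPAI-M total with the named percentage score or scores from 6.3.3.
- State how Q2 + Q4 = 0 is handled, without a blanket exclusion for participants with no work hours.
- Add the eighth SDSF variable to the list in 6.3.4.

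The cost is SAP wording only. No data collection, participant or sample-size consequence follows.
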